CLINICAL STUDY PROTOCOL

A Prospective, Randomized, Double Blind, Parallel Group Study to evaluate a 1:1 Dose Conversion from EPREX to EPIAO in term of Clinical Efficacy and Safety in Subjects with End-Stage Renal Disease on Haemodialysis

Investigational Product	EPIAO
Sponsor	Shenyang Sunshine Pharmaceutical Co., Limited [name]
Protocol Number	EACL-CT-14-003
Study Code	EACL-CT-14-003
Version No	Final Version 1.0, Amendment 8.0
Date	21 May 2018

The following Amendment(s) and Administrative Changes have been made to this protocol since the date of preparation:

Amendment No.	Date of Amendment
01	03 Apr 2015
02	02 Jul 2015
03	01 Oct 2015
04	09 Nov 2015
05	01 Jul 2016
06	02 May 2017
07	29 May 2017
08	21 May 2018

PROTOCOL SYNOPSIS

EudraCT/IND Number:	Not applicable
Protocol Number:	EACL-CT-14-003
Investigational Product:	EPIAO
Active Ingredient(s)/INN:	Recombinant Human Erythropoietin
Study Title:	A Prospective, Randomized, Double Blind, Parallel Group Study to evaluate a 1:1 Dose Conversion from EPREX to EPIAO in term of Clinical Efficacy and Safety in Subjects with End-Stage Renal Disease on Haemodialysis
Study Phase:	Therapeutic equivalence
Indication Under Investigation:	End stage renal disease (Stage 5) receiving haemodialysis
Study Objectives:	
Primary Objective
 
• To evaluate a 1:1 dose conversion from EPREX to EPIAO in term of clinical efficacy and safety in subjects with end-stage renal disease (CKD stage 5) receiving hemodialysis after intravenous (IV) administration. 
Secondary Objectives
 
• To observe the frequency of adverse events (AEs) following EPIAO with and EPREX with respect to their administration.• To monitor the occurrence of anti-epoetin antibodies among subjects following at least 12 months of therapy
Study Design:	This is a prospective, randomized, double blind, parallel group two arm study to evaluate a 1:1 dose conversion from EPREX to EPIAO in term of clinical efficacy and safety in subjects with end-stage renal disease (CKD stage 5) receiving hemodialysis. Subjects should be on a clinically stable haemodialysis for at least 3 months before screening. The eligible subjects will be treated with EPREX for a period of at least 3 months after screening (titration period). The subjects with haemoglobin levels within the target range of 10 to 12.5 g/dl with stable EPREX dosage and intra-individual change in Hb of ≤ 1.2 g/dl over 4 weeks during the titration period will be randomly assigned in a 1:1 ratio to switch

	
to treatment with EPIAO or continue treatment with EPREX. In substantiated cases a prolongation of the titration period is allowed up to maximum of 4 to 5 months on a case to case basis which will be considered as extended titration period. The assessment will be similar to the visit 7 (week 12/Day 84) if there is prolongation of the titration period.

	
Inclusion Criteria at Screening
 
1. Male and female subjects between the age of 18 to 75 years2. Subjects with end stage renal disease (CKD stage 5*) on epoetin treatment for at least 3 months prior to screening3. Subjects with haemoglobin between 10 g/dl to 12 g/dl4. Subjects who are on clinically stable haemodialysis (defined as no clinically relevant changes of dialysis regimen and/or dialyzer) for at least 3 months prior to screening5. Subject who had an adequacy of dialysis treatment measured by Kt/V
a. Kt/V must be ≥ 1.2 for subjects with 3 times of HD/weekb. Kt/V must be ≥ 1.8 for subjects with 2 times of HD/week6. Subjects willing to provide a written informed consent7. Subjects with serum ferritin $\geq 200 \mu\text{g/L}$ and/or transferrin saturation $\geq 20\%$8. Subjects with a life expectancy of more than at least study period in clinical judgment of the investigator
Inclusion/Exclusion Criteria:	
*CKD staging will be based on the five-stage system for classification of CKD based on KDIGO guidelines (page no: 32).
 
GFR will be calculated based on the EPI equation as below
 
$\text{GFR} = 141 \times \min(S_{\text{cr}} / \kappa, 1)^\alpha \times \max(S_{\text{cr}} / \kappa, 1)^{-1.209} \times 0.993^{\text{Age}} \times 1.018 \text{ [if female]} \times 1.159 \text{ [if black]}$
 
where:
 
$S_{\text{cr}}$ is serum creatinine in mg/dL, κ is 0.7 for females and 0.9 for males, α is -0.329 for females and -0.411 for males,

min indicates the minimum of S_{cr} / κ or 1, and max indicates the maximum of S_{cr} / κ or 1.

Eligibility Criteria at Baseline

1. Subjects with stable haemoglobin levels between 10 g/dl to 12.5 g/dl with stable EPREX dosage and intra-individual change in Hb of ≤ 1.2 g/dl over 4 weeks before randomization
2. Subjects with serum ferritin ≥ 200 $\mu\text{g/L}$ and/or transferrin saturation $\geq 20\%$

Patients who don't meet the eligibility criteria at baseline will be considered as screen failures.

Exclusion Criteria at Screening

1. Subjects with anaemia due to other reasons (that is not renal anaemia)
2. Subjects who have undergone blood transfusion within the last 3 months
3. Subjects requiring epoetin dose of > 300 IU/kg/week
4. Subjects with major complication such as severe/chronic infections or bleeding or aluminum toxicity
5. Subjects with suspected or known pure red cell aplasia (PRCA)
6. Subjects with a history of aplastic anaemia
7. Subjects with uncontrolled diabetes (fasting blood glucose > 240 mg/dl) or uncontrolled hypertension (systolic blood pressure > 180 mm Hg, diastolic blood pressure > 110 mm Hg)
8. Subjects with HbA1C $> 6.5\%$
9. Subjects with known hypersensitivity to any of the ingredients of the investigational products, the mammalian cell-derived product or human albumin products
10. Subjects with history of seizure disorder
11. Subjects with hematological disorder (thrombocytopenia: platelet count below $100 \times 10^9/\text{L}$, neutropenia: neutrophil count below $1.0 \times 10^9/\text{L}$ or hemolysis)

	
12. Subjects with hyperparathyroidism (intact parathyroid hormone > 1000 pg/ml)13. Subjects with alanine aminotransferase (ALT), aspartate aminotransferase (AST) and alkaline phosphatase levels 3 × upper limit of normal (ULN) at screening14. Subjects with decompensated congestive heart failure (NYHA class III and IV) within 6 months prior to screening15. Subjects with angina (functional class III and IV) within 6 months prior to screening16. Subjects with myocardial infarction or stroke in the preceding 6 months of screening17. Subjects with active malignancy in the previous 5 years18. Subjects with gastrointestinal bleeding in the past 6 months19. Subjects with immunosuppressive therapy in the previous 3 months20. Subjects with active hepatitis B virus (positive for HBsAg and IgM anti-HBc in Thailand and positive for HBsAg in Russia)21. Subjects with hepatitis C virus (HCV) (positive for Anti-HCV antibody)22. Female subjects who are pregnant, breast-feeding, planning to be pregnant during the study, or women of child-bearing potential (any woman who is not surgically sterile i.e. bilateral tubal ligation, total hysterectomy or < 2 years post menopause) not using a reliable method of double contraception (e.g. condom plus diaphragm, condom or diaphragm plus spermicidal gel/foam, tubal ligation, or stable dose of hormonal contraception) throughout the study period23. Subjects participating in trials involving long acting erythropoietin in the past 6 months before screening and short acting erythropoietin in the past 3 months before screening24. Subjects currently participating or participation in an investigational study within 30 days prior screening
Study Duration:	The duration of the subject participation will be for a maximum of 68 weeks(77weeks in case of extension of titration period)including 4 weeks of screening period, titration period of

	
at least 3 months (maximum duration for 5 months) treatment duration of 26 weeks for efficacy and safety evaluation (weeks 13 through weeks 39) and treatment duration of 26 weeks for immunogenicity evaluation (weeks 40 through weeks 64).
 
In substantiated cases a prolongation of the titration period is allowed up to maximum of 4 to 5 months on a case to case basis which will be considered as extended titration period. The assessment will be similar to the visit 7 (week 12/Day 84) if there is prolongation of the titration period.

Planned Sample Size:	A sample size of 112 subjects per group is calculated to achieve a power of more than 80% for proof of equivalence for both co-primary endpoints. Considering 2 stratification factors i.e. body weight (Kg): ≤58, 59-74 & ≥75, Hb level (g/dl): 10 – 11 & > 11 – 12 and to balance between the two treatment groups in Thailand and Russia, the total number of subjects to be randomized is estimated to be 264 (n=132 subjects in each group) since a drop-out rate of approximately 18% was expected. The subjects will be randomized into two groups (n=132 subjects in each group) in a 1:1 ratio.
Dosage Form, Dose and Route of Administration of IP:	EPIAO injection will be administrated intravenously one to three times a week at the end of dialysis session for a period of 52 weeks. The maximum allowable dose is 300 IU/kg/week.
Dosage Form, Dose and Route of Administration of comparator:	EPIAO injection will be administrated intravenously one to three times a week at the end of dialysis session for a period of 52 weeks. The maximum allowable dose is 300 IU/kg/week.
Study Endpoints:	
Primary endpoint
 
Mean absolute change in haemoglobin level from baseline to 6 months after treatment with EPIAO/EPREX in parallel groups (g/dl).Mean absolute change in weekly epoetin dosage per kg body weight from baseline to 6 months after treatment with EPIAO/EPREX in parallel groups (IU/kg/week) 
Secondary Endpoints:
 
Proportion of subjects hemoglobin values are within 10 - 12 g/dl for the last 4 weeks of the period for assessment of treatment of efficacy and safety (weeks 32-36)

	
• Proportion of subjects with any haemoglobin measurement outside the target range during the double-blind treatment period• Mean hemoglobin and hematocrit levels every 4 weeks within treatment period (52 weeks)• Mean doses of the study products (IU/kg/week) every 4 weeks throughout the study period (52 weeks)• Incidence of blood transfusions 
Safety endpoints:
 
• Incidence and nature of adverse events• Incidence of drug related adverse events• Clinically significant changes in the vital signs, physical and laboratory examination• Number of subjects who prematurely withdrew from the study due to AE and SAE• Number of subjects with presence of anti-erythropoietin antibodies (anti-EPO Ab)
	
The SAS® package (SAS® Institute Inc., USA, and Version 9.2 or higher) will be used for statistical evaluation.
 
Descriptive statistics, such as mean, standard deviation, median, minimum and maximum values will be provided for the continuous variables and the number of observations and percentage will be provided for the categorical variables.

Statistical Analyses:	
Primary Endpoints
 
• Mean absolute change in haemoglobin level from baseline to 6 months after treatment with EPIAO/EPREX in parallel groups (g/dl).• Mean absolute change in weekly epoetin dosage per kg body weight from baseline to 6 months after treatment with EPIAO/EPREX in parallel groups (IU/kg/week) 
The ANCOVA will be performed based on the normality of data for mean change between baseline to 6 months of EPIAO and EPREX with center, Hb level and weight as covariates. The 95% confidence intervals will be calculated for the treatment differences and is compared with pre-defined acceptance ranges: ± 0.5 g/dl for hemoglobin.

The ANCOVA will be performed based on the normality of data for mean change in weekly epoetin dosage per kg body weight baseline to 6 months treatment with EPIAO and EPREX with center, Hb level and weight as covariates. The 95% confidence intervals will be calculated for the treatment differences and is compared with pre-defined acceptance ranges: ± 45 IU/kg/week for dosage.

Secondary Endpoints

- Proportion of subject's hemoglobin values are within 10 - 12 g/dl for the last 4 weeks of the period for assessment of treatment efficacy and safety (weeks 32-36)
- Proportion of subjects with any haemoglobin measurement outside the target range during the double-blind treatment period
- Mean hemoglobin and hematocrit levels every 4 weeks within treatment period (52 weeks)
- Mean doses of the study products (IU/kg/week) every 4 weeks throughout the study period (52 weeks)
- Incidence of blood transfusions

The appropriate descriptive statistics or frequency and percentages will be presented for the secondary end point. Other analysis will be carried out as deemed appropriate.

Safety Endpoints

- Incidence and nature of adverse events
- Incidence of drug related adverse events
- Clinically significant changes in the vital signs, physical and laboratory examination
- Number of subjects who prematurely withdrew from the study due to AE and SAE
- Number of subjects with presence of anti-erythropoietin antibodies (anti-EPO Ab)

Safety will be assessed by physical examination, vital sign, laboratory test, immunogenicity and adverse event recording. Summary statistics will be provided for the lab, ECG, physical examination, immunogenicity and vital signs data. Frequency and percentage of the incidence of adverse event, nature of adverse event and incidence of drug related adverse event will be

presented in the treatment group. Summary statistics will be presented for the occurrence of PRCA.

Proportion of subject who used concomitant medication during the study period will be computed by treatment group, classified by World Health Organization Drug Dictionary enhanced (WHO - DDE) Preferred Names. Concomitant medication will be coded using the WHO - DD enhanced version, classified by preferred names, and the categories tabulated and summarized.

An interim analysis will be conducted to evaluate the therapeutic equivalence of EPIAO with the standard treatment EPREX after a treatment period of 24 weeks.

TABLE OF CONTENTS

1	INTRODUCTION AND BACKGROUND INFORMATION.....	55
1.1	NAME OF INVESTIGATIONAL PRODUCT	56
1.1.1	Description	56
1.1.2	Intended Use under Investigation	57
1.1.3	Nonclinical Studies	57
1.1.4	Clinical Experience	59
1.2	STUDY RATIONALE	62
1.3	RISKS AND BENEFITS FOR STUDY SUBJECTS	63
1.4	ROUTE, DOSAGE, DOSAGE REGIMEN, TREATMENT PERIOD	64
1.5	COMPLIANCE STATEMENT, ETHICS AND REGULATORY COMPLIANCE.....	64
1.5.1	Subject Confidentiality	64
1.5.2	Informed Consent Procedure	64
1.5.3	Regulatory Compliance	65
2	STUDY OBJECTIVES AND HYPOTHESES.....	66
2.1	STUDY OBJECTIVES	66
2.1.1	Primary Objective	66
2.1.2	Secondary Objectives	66
3	STUDY DESIGN.....	66
3.1	OVERALL STUDY DESIGN	66
3.1.1	Study Type	66
3.1.2	Treatment Groups	66
3.1.3	Study Endpoints	67
3.1.4	Duration of the Study	68
3.1.5	Duration of Subject Participation	68
3.1.6	Discontinuation Criteria	68
4	STUDY POPULATION	69
4.1	ENROLLMENT.....	69
4.1.1	Inclusion Criteria at Screening	69
4.1.2	Eligibility criteria at Baseline	70
4.1.3	Exclusion Criteria at Screening	70
4.2	REMOVAL OF SUBJECTS FROM THERAPY	71
4.2.1	Reasons for Withdrawal/Early Discontinuation	71
4.2.2	Withdrawal Procedures	72
4.2.3	Subject Replacement	72
4.2.4	Subject Re-screening Procedures	72

5 TREATMENTS ADMINISTERED	72

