The guidelines recommends to perform a ‘maintenance phase’ study using IV epoetin (e.g. in a haemodialysis population) for demonstration of similar efficacy of administration between the bio-similar product and the reference bio-similar product. The recommended choice of the reference product for erythropoietin bio-similar products, epoetin alfa is EPREX.

The maintenance phase study is designed to minimise baseline heterogeneity and carry over effects of previous treatments. Subjects included in a maintenance phase study will be optimally titrated on the reference product (EPREX) (stable haemoglobin in the target range on stable epoetin dose and regimen without transfusions) for duration of at least 3 months. In substantiated cases a prolongation of the titration period is allowed up to maximum of 4 to 5 months on a case to case basis which will be considered as extended titration period. The assessment will be similar to the visit 7 (week 12) if there is prolongation of the titration period. Thereafter, study subjects should be randomised to the EPIAO or continued on EPREX, maintaining their pre-randomisation epoetin dosage, dosing regimen and route of administration (IV).

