5.1.7 Dosing Schedule, Selection and Timing of dosing

Study drugs have to be administered in strict accordance with approved protocol.

Treatment arm A

EPIAO group (test product) having 132 subjects will receive EPIAO, one to three times a week, intravenously for period of 52 weeks at the end of dialysis session

Treatment arm B

EPREX group (reference product) having 132 subjects will receive EPREX, one to three times a week, intravenously for period of 52 weeks at the end of dialysis session

The blood pressure will be monitored after the haemodialysis procedure and if the blood pressure is within the normal range then the study medication will be administrated by the study nurse or designee. If systolic pressure >160 mm of Hg, the blood pressure will be monitored after half an hour. If the BP does not decrease then the subject will be asked to come the next day for drug administration.

The dose will be adjusted individually to maintain haemoglobin at a level not exceeding 12 g/dl. The required dose will be calculated based on the haemoglobin.

Dosage adjustment:

Titration period:

During titration period, EPREX will be administered one to three times weekly as per last dose which subject received previously before screening, for subject who are already on treatment. EPREX will be administered one to three times weekly as per Hb value at screening and as per PI discretion. The dose received by the subject at screening will be taken as the "basic initial dose" for all subjects. An increase or decrease of 2000 IU per week will be allowed for dose adjustment to maintain subject's Hb value within target range (10 – 12.5 g/dl). At this point, the "stable dose" of EPREX for each patient will be determined. The stable dose of EPREX / EPIAO will be calculated as IU/kg/week before the start of the treatment period and captured in the eCRF. In substantiated cases, a prolongation of the titration period is allowed up to maximum of 4 to 5 months on a case to case basis which will be considered as extended titration period.

During treatment period, subjects randomized to EPREX arm will continue on an equivalent dose of EPREX as during the titration period. Subjects randomized to EPIAO arm will receive EPIAO treatment 1:1 dose conversed from that of EPREX during the titration period. If subject's Hb value is out of target range, an increase or decrease of 2000 IU per week is allowed for dose adjustment. The maximum allowable dose is 300 IU/kg/week.

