Treatment period:

The dose should be adjusted for each patient to achieve and maintain hemoglobin levels between 10-12 g/dl. The maximum dose of study drug is 300 IU/kg.

[figure not shown]
The investigator can adjust the dose by their own decision based on the best interest and safety of the subject and in any time

Two key factors will be considered for dose adjustment during the study period

1. Hemoglobin level at current visit
2. Changes in hemoglobin over past 4 weeks

- If haemoglobin decreases more than 1 g/dl over the past 4 weeks and current haemoglobin level is < 10.5 g/dl, the dosage may be raised by 25% of the last dose received by the subject (A).
- If haemoglobin decreases more than 1 g/dl over the past 4 weeks and current haemoglobin level is between 10.5 g/dl to 12.0 g/dl, the last dose received by the subject should be continued (B).
- If haemoglobin decreases more than 1 g/dl over the past 4 weeks but current haemoglobin is between 12.1 to 13.0 g/dl, the dose should be reduced by 25% of the last dose received by the subject (C).
- If haemoglobin decreases or an increase between 1.0 g/dl and current haemoglobin value is less than 10.5 g/dl, the dosage may be raised by 25% of the last dose received by the subject (D).
- If haemoglobin decreases or an increase between 1.0 g/dl and the current hemoglobin value is between 10.5 to 12.0 g/dl, the last dose received by the subject should be continued (E).
- If haemoglobin decreases or increase between 1.0 g/dl but the current haemoglobin is between 12.1 to 13.0 g/dl, the dose should be reduced by 25% of the last dose received by the subject (F).
- If haemoglobin increases more than 1 g/dl over the past 4 weeks and current haemoglobin is < 10.5 g/dl, the last dose received by the subject should be continued (G).
- If haemoglobin increases more than 1 g/dl over the past 4 weeks and haemoglobin level is between 10.5 to 12.0 g/dl, the last dose received by the subject should be continued (H).
- If haemoglobin increases more than 1 g/dl over the past 4 weeks but current haemoglobin is between 12.1 to 13.0 g/dl, the dose should be reduced by 25% of the last dose received by the subject (I).
- If current haemoglobin level is greater than 13.0 g/dl, not depending on the change of haemoglobin in the past 4 weeks, dose should be temporarily withheld until the haemoglobin begins to decrease between 10.5 and 12.0 g/dl, at which point therapy should be reinitiated at 25% reduced from the previous dose (J).

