6.3 Randomization / Visit 8 (Day 91+3 / Week 13)

After the titration period of at least 3 months (or extended titration period of 2 months) with window period of ± 2 days, subjects who successfully fulfill the eligibility criteria at any of baseline visits will qualify for randomization and will be randomized to appropriate arm as per the study design. A negative serum pregnancy test is a must for females of child-bearing potential prior to randomization. If the subjects do not meet the eligibility criteria at the baseline visit, they will be considered as screen failures and will be discontinued from the study.

At this visit, vital signs will be recorded and physical examination will be done. AEs and concomitant medication will be recorded. The blood pressure will be monitored after the haemodialysis procedure and if the blood pressure is within the normal range then the study medication will be administrated by the study nurse or designee. If systolic pressure >160 mmHg, the blood pressure will be monitored after half an hour. If the BP does not decrease then the subject

will be asked to come the next day for drug administration. Assessments will be completed as per the study visit plan.

The following assessments will be performed;

- Demographic data (body weight: pre and post hemodialysis)
- Review and document eligibility criteria (Hb should be within the target range of 10 to 12.5 g/dl at visit 8 and intra individual change in Hb of ≤ 1.2 g/dl over previous 4 weeks i.e. over V5/V6/V7 or V7/EV8/EV9 or EV9/EV10/EV11).
- Serum pregnancy test
- Vital signs
- Adverse events
- Concomitant medication
- Physical examination
- Randomization of subjects
- CBC
- BUN (pre and post hemodialysis)
- Iron study
- Immunogenicity testing for anti-EPO antibody
- Adequacy of dialysis measurement by Kt/V formula

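### The Hb target range changes across the switch: a subject steady at 12.1-12.5 g/dl is accepted as stable and in target at Visit 8, then meets a dose-reduction rule on the same Hb one week later

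*Protocol*

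**What the plan says.** Before the switch, the range is 10 to 12.5 g/dl throughout:

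- Titration (section 5.1.7) adjusts the dose to "maintain subject's Hb value within target range (10 – 12.5 g/dl", and the dose reached becomes the subject's stable dose.
- Eligibility at baseline (synopsis and section 4.1.2) requires "Subjects with stable haemoglobin levels between 10 g/dl to 12.5 g/dl with stable EPREX dosage".
- At randomisation (section 6.3), "Hb should be within the target range of 10 to 12.5 g/dl at visit 8". The synopsis design paragraph and sections 3.1.2 and 6.2 also call 10 to 12.5 the target range.

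Elsewhere the upper limit is 12:

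- Sections 1.4 and 5.1.7 say that dosing keeps Hb from exceeding 12 g/dl.
- The treatment-period text in 5.1.7 adjusts the dose "to achieve and maintain hemoglobin levels between 10-12 g/dl".
- For an Hb that has moved by no more than 1.0 g/dl in four weeks, rule F says that if "the current haemoglobin is between 12.1 to 13.0 g/dl, the dose should be reduced by 25% of the last dose received". Rule D says that if "current haemoglobin value is less than 10.5 g/dl, the dosage may be raised by 25% of the last dose received". Rule E continues the dose only from 10.5 to 12.0.
- The Hb strata (synopsis and section 9.8) are 10-11 and above 11 to 12.
- The first secondary endpoint (section 3.1.3) counts Hb within 10-12 g/dl. The second counts Hb outside the target range without saying which range.

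Dose adjustment is scheduled from Visit 9 (Week 14), one week after Visit 8 (Week 13).

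**The concern.** Change in weekly dose per kg is a co-primary endpoint, and the design depends on the baseline dose being a maintenance dose. At 12.1-12.5 g/dl the run-in rules treat the dose as stable and the treatment rules call for a reduction, with no change in the subject. Part of that subject's dose change then reflects the entry range and not the product, and the Hb movement that follows enters the other co-primary. Investigators must also choose between ranges, and centres may choose differently. The endpoint on Hb outside the target range gives a different count depending on whether the limit is 12 or 12.5.

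**Working it through.** **1. The ranges side by side (no assumption needed).**

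| Use | Hb (g/dl) | Section |
|---|---|---|
| Screening | 10-12 | 4.1.1 |
| Titration target | 10-12.5 | 5.1.7 |
| Baseline and Visit 8 | 10-12.5 | 4.1.2, 6.3 |
| Strata | 10-11, >11-12 | 9.8 |
| Treatment target | 10-12 | 5.1.7 |
| Dose continued (rule E) | 10.5-12.0 | 5.1.7 |
| Dose may be raised (rule D) | <10.5 | 5.1.7 |
| Dose should be reduced (rule F) | 12.1-13.0 | 5.1.7 |
| First secondary endpoint | 10-12 | 3.1.3 |

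The accepted range is 2.5 g/dl wide. The high zone (12.1-12.5) takes 0.4 of it and the low zone (10.0 to 10.5) takes 0.5.

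**2. Share of subjects in each zone.** The protocol states no such figure, so there is nothing to reproduce. Assume Hb at Visit 8 is normal with mean m and SD s, truncated to the accepted range and recorded to 0.1 g/dl (cuts 9.95, 10.45, 12.05, 12.55). Then

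- low = [F(10.45) - F(9.95)] / [F(12.55) - F(9.95)]
- high = [F(12.55) - F(12.05)] / [F(12.55) - F(9.95)]

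Example with m = 11.0 and s = 0.6: F = 0.0401, 0.1797, 0.9599, 0.9951. Low = 0.1396/0.9550 = 14.6%, high = 0.0352/0.9550 = 3.7%, total 18.3%, or 48 of 264.

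| Mean | SD | Low | High | Total |
|---|---|---|---|---|
| 11.0 | 0.5 | 12.0% | 1.7% | 13.7% |
| 11.25 | 0.5 | 5.1% | 5.1% | 10.1% |
| 11.4 | 0.6 | 5.1% | 11.6% | 16.6% |
| 11.0 | 0.94 | 18.0% | 10.1% | 28.1% |
| 11.4 | 0.94 | 11.4% | 16.2% | 27.6% |

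Over means 11.0-11.4 and SDs 0.5-0.94, the high zone holds about 2-16% (roughly 5 to 43 of 264) and both zones together about 10-28% (27 to 74). The upper SD comes from the other product's switch study described in section 1.1.4 (10.94 ± 0.84 and 11.02 ± 0.94 g/dl). The lower one is an assumed tighter case, because these subjects have passed a stability gate. Simulating the gate itself gives 10-13% in either zone at Visit 9 for a total SD near 0.5, and 20-26% for 0.7-0.94.

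**3. Effect on the dose endpoint.** Assume a mean dose of 100 IU/kg/week and a full 25% step for every subject in either zone. The added SD is about 25 × √p: 25 × √0.10 = 7.9, and 25 × √0.28 = 13.2 IU/kg/week.

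The protocol gives no SD for the dose change. With 112 per group, margin 45, a 95% confidence interval and no true difference, 80% power on this endpoint corresponds to SD = 45 / [(1.960 + 1.282) × √(2/112)] = 103.9. Adding 13.2 in quadrature gives √(103.9² + 13.2²) = 104.7, and power = 2Φ(45/(104.7 × 0.1336) - 1.960) - 1 = 79.1%. From an SD of 80, power moves from 97.6% to 97.2%.

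**The case against.** Much can be said against a stronger reading, and most of it stands.

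- A reader might infer that about a fifth of randomised subjects will have their dose changed by rule at Visit 9. The documents give no Hb distribution, so any single share is an assumption. The low-side rule says only that the dose may be raised, and its zone lies inside the 10-12 target. Section 5.1.7 calls all the criteria recommendations and leaves the investigator free to depart from them.
- A reader might infer that section 1.2 is contradicted, because subjects go on "maintaining their pre-randomisation epoetin dosage, dosing regimen and route of administration (IV". That sentence describes what happens at randomisation, and the 1:1 conversion does it. It does not freeze later doses, and dose change is measured because titration continues.
- A reader might infer bias. Both arms face the same rules under blinded investigators, so the mismatch alone does not shift the between-arm difference.
- Hb level is an ANCOVA covariate. If it enters as a continuous term, linear adjustment brings the added SD from 10-13 down to about 7-7.6 IU/kg/week (SDs 0.6-0.94).
- Doses round up to 2000 IU multiples. If this applies to the weekly total, a 60 kg subject on 100 IU/kg/week has 6000 IU; 75% is 4500, which rounds back to 6000. The 25% step is therefore an upper case.
- Section 5.1.7 also allows a 2000 IU step in the treatment period only when Hb is out of target range. Read with 10-12.5, that leaves accepted subjects unchanged.
- The strata match the screening range. If they refer to screening Hb, the gap above 12 closes, but the protocol does not say which measurement is used.

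None of this removes the conflict at 12.1-12.5 g/dl. The 2000 IU rule helps only if its target range is 10-12.5, while the treatment-period text in the same section says 10-12. Discretion leaves each investigator to decide which range applies.

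**Conclusion.** The conflict is in the protocol text and needs no assumption: 10 to 12.5 g/dl up to Visit 8, and 12 as the upper limit for treatment-period dosing, the strata and the first secondary endpoint. It is firm at 12.1-12.5 g/dl; below 10.5 there is only a permissive zone within target. The shares (about 2-16% at 12.1-12.5, about 10-28% in both zones) rest on the assumed truncated normal with mean 11.0-11.4 and SD 0.5-0.94. Narrower or flatter distributions widen the total to about 1% (mean 11.25, SD 0.3) or 36% (uniform). The consequence is extra, non-differential dose and Hb movement in both arms, costing at most about one point of power on the dose endpoint under the assumptions above. It does not threaten the equivalence conclusion by itself. It merits correction because the conflicting rule acts directly on a co-primary endpoint and leaves one secondary endpoint undefined.

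**What to change.** Reconcile the synopsis and sections 1.4, 3.1.2, 3.1.3, 4.1.2, 5.1.7, 6.2, 6.3 and 9.8 so that one target range governs titration, baseline acceptance, stratification, dose adjustment and the endpoint on Hb outside the target range. State which Hb measurement defines the stratum. Which range is meant is for the clinical team to decide.

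For subjects already randomised, pre-specify one sensitivity analysis of both co-primaries in those with Visit 8 Hb 10.5-12.0 g/dl, and report by arm the number whose dose changed at Visit 9. Selecting on a baseline value keeps the comparison randomised, and the data are already collected.

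The cost is amendment wording and one extra analysis on a smaller subset (about 72-90% of subjects under the assumptions above). Depending on the range chosen, a few more subjects may fail the run-in.
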